8. SELECTION AND WITHDRAWAL OF SUBJECTS

8.1. Subject Inclusion Criteria

- Male or non-pregnant female at least 18 years of age at time of consent
- One or both eyes having a history of recurrent non-infectious uveitis affecting the posterior segment of the eye with or without anterior uveitis ≥ 1 year duration.
- During the 12 months prior to enrollment (Day 1),
the study eye has either received treatment:
 - systemic corticosteroid or other systemic therapies given for at least 3 months, and/or
 - at least 2 intra- or peri-ocular injections of corticosteroid for management of uveitis
- OR the study eye has experienced recurrence:
 - at least 2 separate recurrences of uveitis requiring systemic, intra- or peri-ocular injection of corticosteroid
- At the time of enrollment (Day 1), study eye has < 10 anterior chamber cells/HPF and a vitreous haze \leq grade 2.
- Visual acuity of study eye is at least 15 letters on the ETDRS chart
- Subject is not planning to undergo elective ocular surgery during the study
- Subject has ability to understand and sign the Informed Consent Form
- Subject is willing and able to comply with scheduled visits, treatment plan, laboratory tests, and other study procedures

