13. ASSESSMENT OF EFFICACY

13.1. Primary Efficacy Endpoint

The Primary Efficacy Endpoint is defined as the proportion of subjects who have a recurrence of uveitis in the study eye within 6 months following treatment. Recurrence is defined as:

- A ≥ 2 step increase in the number of cells in the anterior chamber per high powered field (1.6 X using a 1-mm beam) ([Hogan 1959](#)), compared to baseline or any visit time point prior to Month 6
OR
- An increase in the vitreous haze of ≥ 2 steps ([Nussenblatt 1985](#)), compared to baseline or any visit time point prior to Month 6
OR
- A deterioration in visual acuity of at least 15 letters BCVA, compared to baseline or any visit time point prior to Month 6

Any criterion used to define recurrence must be attributable only to noninfectious uveitis. To prevent post-procedural inflammatory reactions from being reported as uveitis recurrences, assessments for recurrence of uveitis begin after study Day 7 visit.

Refer to Appendix 2 ([Section 19](#)) for additional information.

13.2. Exploratory Efficacy Endpoints:

Exploratory endpoints include:

- Proportion of subjects who have a recurrence of uveitis in the study eye within 12 months or 36 months
- Proportion of subjects who have a recurrence of uveitis in the fellow eye (within 6 months, 12 months or 36 months)
- Mean change from baseline in BCVA letter score in the study eye (at 6 months, 12 months or 36 months)
- Number of recurrences of uveitis (within 6 months, 12 months or 36 months)
- Time to recurrence of uveitis (within 6 months, 12 months or 36 months)
- Number of adjunctive treatments required to treat recurrences of uveitis (within 6 months, 12 months or 36 months)
- Resolution of macular edema, as measured by OCT imaging (at 6 months, 12 months or 36 months)

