19. APPENDIX 2: METHODS OF CLINICAL EVALUATION

19.1. Ophthalmoscopy and Grading of Vitreous Haze

[figure not shown]
Ophthalmoscopy will be performed to assess retinal and choroid appearances and vitreous haze (Nussenblatt 1985). Indirect ophthalmoscopy will be performed for each eye with pupil dilation and should be completed after IOP measurement has been completed.

Vitreous Haze Grading Scale

The following scale will be used to define the extent of vitreous haze:

Absent	Clear view of optic disc, retinal vessels and nerve fiber layer
Trace	Slight blurring of optic disc margin and of normal striations and reflex of nerve fiber layer
1+	Mild blurring of optic disc margin and slight loss of retinal vessel definition
2+	Moderate blurring of optic disc margin and loss of retinal vessel definition
3+	Optic nerve head and large vessels visible but borders quite (very) blurry
4+	Optic nerve head obscured

Figure 3: Vitreous Haze Scoring Convention

[figure not shown]
Anterior Chamber Cells Grading Scale

Anterior chamber cells will be measured using a Haag/Streit or similar slit lamp at high magnification (1.6 X) 1-mm beam. The same instrument, and when possible the same examiner should be used on each patient throughout the study. Assessment will be made using the following scale (Jabs 2005).

Field size: 1 mm by 1 mm slit beam

0	<1 cells/hpf
0.5+	1-5 cells/hpf
1+	6-15 cells/hpf
2+	16-25 cells/hpf
3+	26-50 cells/hpf
4+	>50 cells/hpf

Figure 4: Anterior Chamber Cell Scoring Convention

Fundus Examination

The fundus assessments should be conducted using indirect ophthalmoscopy with a 20 diopter, 28 diopter, or 30 diopter condensing lens. In order to minimize variability, every effort should be made to have a single examiner conduct all assessments on a given subject.

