3.2. Study Endpoints

The primary efficacy endpoint is the proportion of subjects who have a recurrence of uveitis in the study eye within 6 months after receiving study treatment. Recurrence is captured on the Recurrence of Uveitis eCRF page and, for the US/FDA, is defined as:

- An increase in the vitreous haze of ≥ 2 steps, compared to baseline or any visit time point prior to Month 6
OR
- A deterioration in visual acuity of at least 15 letters BCVA, compared to baseline or any visit time point prior to Month 6

Any criterion used to define recurrence must be attributable only to noninfectious uveitis. To prevent post-procedural inflammatory reactions from being reported as uveitis recurrences, assessments for recurrence of uveitis begin after the study Day 7 visit.

The exploratory efficacy endpoints include:

- Proportion of subjects who have a recurrence of uveitis in the study eye within 12 months and 36 months
- Proportion of subjects who have a recurrence of uveitis in the fellow eye (within 6 months, 12 months and 36 months)
- Mean change from baseline in best-corrected visual acuity (BCVA) letter score in the study eye (at 6 months, 12 months and 36 months)
- Number of recurrences of uveitis (within 6 months, 12 months and 36 months)
- Time to recurrence of uveitis in the study eye (within 6 months, 12 months and 36 months)
- Number of adjunctive treatments required to treat recurrences of uveitis (within 6 months, 12 months and 36 months)
- Resolution of macular edema, as measure by OCT imaging (at 6 months, 12 months and 36 months)

In addition, the following safety endpoints will be included in the analysis:

- Systemic adverse events
- Ocular adverse events, including intra-ocular pressure (IOP) elevation
- Medications/procedures required to control elevated IOP
- Development or worsening of cataract
- Cataract-related procedures
- Clinically significant ocular changes
- Treatment related adverse events

4. General Statistical Considerations

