6.2. Baseline Disease and Ocular Characteristics

A summary of baseline disease characteristics will be presented for the study eye and fellow eye for the ITT and Safety populations. Summaries will be generated for the Safety population only if there are randomized subjects who do not receive treatment. The baseline characteristics consist of study eye, randomization strata for systemic treatment to control uveitis, duration of uveitis (years), number of recurrences in the last 12 months, lens status, presence of cataract, history of vitrectomy procedure and history of incisional surgery to control elevated IOP.

Duration of uveitis is calculated as (Screening date – date of onset of uveitis +1)/ 365.25 and will be summarized using descriptive statistics. For partial onset dates, a missing month will be imputed as January and a missing day will be imputed as the first of the month.

The number and percentage of subjects by study eye (OD, OS), randomization strata (Not receiving systemic treatment, Receiving systemic treatment – corticosteroid therapy, Receiving systemic treatment – immunosuppressive therapy), duration of uveitis (< 2 years, 2 to 5 years, > 5 years), number or recurrences (<= 2, >2), lens status (phakic, aphakic, and pseudophakic), presence of cataract for subjects with a lens status of phakic, history of vitrectomy procedure, and history of incisional surgery to control elevated IOP will also be reported. Percentages will be based on the total number of subjects in the ITT or Safety population, as applicable.

In addition, baseline ocular characteristics will be summarized for the study eye. The baseline ocular characteristics consist of severity of macular edema, IOP (mmHg), and BCVA (letters). Baseline IOP and BCVA will be summarized using descriptive statistics. The number and percentage of subjects by baseline severity of macular edema (CSFT < 300 microns, CSFT >= 300 microns) will also be reported.

Subject baseline disease and ocular characteristics will be presented in a listing.

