8.1. Primary Efficacy Endpoint

[figure not shown]
The primary efficacy endpoint is defined as the proportion of subjects who have a recurrence of uveitis in the study eye within 6 months following treatment. As noted in section 4, all recurrence assessments (including unscheduled visits) on or before the upper limit of the 6 month visit window (Day 208) will be considered. Recurrence is captured on the Recurrence of Uveitis eCRF page and, for the US/FDA, is defined as:

- An increase in the vitreous haze of ≥ 2 steps ([Nussenblatt 1985](#)), compared to baseline or any visit time point prior to Month 6
OR
- A deterioration in visual acuity of at least 15 letters BCVA associated with recurrence of uveitis, compared to baseline or any visit time point prior to Month 6

Any criterion used to define recurrence must be attributable only to non-infectious uveitis. To prevent post-procedural inflammatory reactions from being reported as uveitis recurrences, assessments for recurrence of uveitis will begin after the study Day 7 visit.

The definition of a ≥ 2 step increase in vitreous haze is detailed in the diagram below.

Vitreous Haze: ≥ 2 step increase

* Nussenblatt et al 1985

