Additionally, for missing data due to any reason, sensitivity analyses will be conducted by using multiple imputation (MI) methods. The list of subjects who will have their Month 6 (or 12 or 36) value imputed using MI methods will be determined prior to each database lock. A fully conditional specification (FCS) imputation method will be used to impute missing recurrence values. Five imputations will be performed to obtain five complete data sets. The volume of missing data will be assessed prior to unmasking at Month 6 and the number of imputations may be increased, if necessary. The SAS procedure MI will be used to generate the imputed data sets. The following variables will be included in the imputation model: recurrence, age, gender, treatment group, systemic treatment at study entry (stratification factor), duration of disease (years) in the study eye, number of recurrences in study eye within the 12 months prior to screening, and bilateral uveitis history (yes/no). The imputed datasets will be analyzed by a logistic regression model with recurrence as the dependent term and treatment as the independent term. Using the SAS procedure MIANALYZE, results from the logistic regression analysis of the five imputed data sets will be combined to obtain overall estimates [SAS/STAT User Guide, version 9.3]. Additional details are provided in [Appendix 13.2](#). Note: for this sensitivity analysis, subjects who have not previously experienced a recurrence and who take prohibited medications prior to the time point of interest will have their Month 6 (or 12 or 36) value imputed as a recurrence as described in [Section 8.1.2](#).

The primary efficacy endpoint will be also analyzed with logistic regression with recurrence as the dependent term and treatment as the independent term, and including systemic treatment at study entry (stratification factor) as a covariate.¹

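### An eye that enters at haze 2+ and never falls below it meets the haze criterion only at 4+, and no planned efficacy analysis relates baseline haze to recurrence

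*Protocol*

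**What the plan says.** Entry. Protocol 8.1 requires that on Day 1 the "study eye has < 10 anterior chamber cells/HPF and a vitreous haze" of grade 2 or lower. Eyes graded absent, trace, 1+ or 2+ may therefore enter.

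Scale. Protocol 19.1 and SAP 9.2.5 print six ordered grades: absent, trace, 1+, 2+, 3+ and 4+. Grade 3+ is "Optic nerve head and large vessels visible but borders quite (very) blurry" and 4+ is "Optic nerve head obscured".

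Endpoint. SAP 8.1 counts "An increase in the vitreous haze of ≥ 2 steps" as recurrence, and Protocol 13.1 measures the rise "compared to baseline or any visit time point prior to Month 6". No criterion uses an absolute haze level or requires haze to clear. The other clinical component in the US definition is a 15-letter BCVA loss; the Protocol definition adds anterior chamber cells. SAP 8.1.2 also imputes recurrence for missing Month 6 examinations and for prohibited systemic or local medication. For the US endpoint it exempts topical steroids.

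Use of baseline haze.
- SAP 4.2 stratifies randomization on systemic treatment only.
- The supportive logistic regression in SAP 8.1.3 is fitted "including systemic treatment at study entry (stratification factor) as a covariate", with no other baseline term.
- The multiple imputation model in SAP 8.1.3 and 13.2 has no haze term.
- SAP 8.1.4 does not name haze as a subgroup, though its list is introduced as not exhaustive.
- SAP 6.2 gives a closed list: "The baseline ocular characteristics consist of severity of macular edema, IOP (mmHg), and BCVA (letters".
- SAP 9.2.5 tabulates haze grade by visit, eye and treatment group as a safety summary.

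**The concern.** The starting grade decides how much deterioration is needed before the haze criterion can be met. Haze is one of only two clinical components of the US endpoint. The other, BCVA, is summarized at baseline and used as a subgroup for the primary endpoint; haze gets neither.

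What is at stake is interpretation. Protocol 9.10.1 says prior treatment aims for a relatively quiet eye at enrollment, and a reader will tend to take recurrence-free as meaning quiet. An eye at 2+ throughout can be recurrence-free, and nothing planned shows how many of the successes in each arm are of this kind.

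**Working it through.** **1. Plan's own figure.** Protocol 14.1 and SAP 4.1 give recurrence-free rates of 0.600 (sham, n = 40) and 0.880 (FAI, n = 80), two-sided 0.05, continuity-corrected chi-square, 89% power.
- Pooled rate = (24 + 70.4)/120 = 0.787
- Null SE = sqrt(0.787 × 0.213 × (1/40 + 1/80)) = 0.0793
- Alternative SE = sqrt(0.6 × 0.4/40 + 0.88 × 0.12/80) = 0.0856
- Continuity correction = 0.5 × (1/40 + 1/80) = 0.01875
- Power = Φ[(0.28 − 0.01875 − 1.96 × 0.0793)/0.0856] = 0.892

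The stated power reproduces and is not in question.

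**2. Reachability of the haze criterion.** Counting steps along the printed grades, from the lowest earlier grade:

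| Lowest earlier grade | Does not count | Counts |
|---|---|---|
| Absent | absent, trace | 1+ to 4+ |
| Trace | trace, 1+ | 2+ to 4+ |
| 1+ | 1+, 2+ | 3+, 4+ |
| 2+ | 2+, 3+ | 4+ only |

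The step diagram in SAP 8.1 is not shown in the text available. The last row does not depend on it: however trace is counted, only 4+ is two steps above 2+. Because any earlier visit can serve as comparator, an eye that goes from 2+ to 1+ and then to 3+ does count. The gap concerns eyes that never fall below 2+.

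**3. Direction and scale of misreading.** Suppose k of 40 sham eyes and m of 80 FAI eyes are recurrence-free but at 2+ or worse at Month 6. Counting them as failures would change the FAI − sham difference by 2.5k − 1.25m points (1/40 = 2.5 points; 1/80 = 1.25 points). If such eyes are commoner in sham (k/40 > m/80), the change is positive, so the planned scoring dilutes the effect.

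**4. Chance imbalance.** The share q entering at 2+ is not documented; 20% to 40% is assumed. The 95% range of imbalance is 1.96 × sqrt(q(1 − q)(1/80 + 1/40)): ±15.2 points at q = 0.2, ±17.4 at 0.3 and ±18.6 at 0.4.

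To turn this into a shift in the treatment difference, assume recurrence is lower by g_S in hazy sham eyes and by g_F in hazy FAI eyes. With 12% planned FAI recurrence, g_F cannot exceed 0.12/(1 − q): 15, 17 and 20 points at the three values of q. The 95% shift is 1.96 × sqrt(q(1 − q)(g_F²/80 + g_S²/40)).
- q = 0.2, g_S = 0.20, g_F = 0.15: 1.96 × sqrt(0.16 × 0.00128) = 2.8 points
- q = 0.4, g_S = 0.30, g_F = 0.20: 1.96 × sqrt(0.24 × 0.00275) = 5.0 points

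For comparison, the 95% half-width of the planned difference is 1.96 × 0.0856 = 16.8 points. The shift is a component of that error, not an addition to it.

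**5. Gain from adjustment.** In simulated logistic regressions at 40% versus 12% recurrence, with about 3000 runs per setting, adding a haze term moved power from 93.6% to 94.5%, 93.4% to 93.7% and 92.9% to 93.4% in three assumed settings. At 30% versus 13% it moved from 58.4% to 59.5%. Across assumed inputs the gain is about 0 to 2 points.

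**6. Room in the model.** Expected recurrences are 80 × 0.12 + 40 × 0.40 = 9.6 + 16 = 25.6, about 26. Treatment (1), stratum (2) and a two-level haze term (1) make four coefficients, about 6.4 events each. A three-level haze term makes five, about 5.1 each.

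**The case against.** A reader might infer that nothing planned would reveal an imbalance in baseline haze. The documents do not support that. SAP 9.2.5 tabulates haze at each scheduled visit by arm, and the visit table in SAP section 4 includes Day 1. The table covers treated subjects only, but it would show an imbalance. It would not link haze to recurrence status.

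A reader might also infer that persistently inflamed eyes generally count as successes. That is too strong. Such an eye must stay below 4+, lose fewer than 15 letters from uveitis, complete the Month 6 examinations and receive no prohibited systemic or injected medication, subject to the pre-lock review in SAP 8.1.2 of which medications matter. Entry systemic and topical treatment must end within three months (Protocol 9.10.1). Under the Protocol definition, anterior chamber cells are a further route. The US exemption for topical steroids leaves an opening, although Protocol 5.2 itself calls topical delivery ineffective in intermediate and posterior uveitis.

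A third tempting reading is that the primary result is biased toward FAI. If persistent haze is commoner in sham, the bias runs the other way. Chance imbalance can go in either direction and is already covered by the test's error rate.

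Finally, the covariate costs a parameter when events are few, and the 2+ group may have very few. This stands as a caution on coding. What survives is narrow: no efficacy output connects haze at entry, or haze at Month 6, with being recurrence-free.

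**Conclusion.** The point holds in a limited form. On the printed scale, an eye that never falls below 2+ can stay at 2+ or reach 3+ without a haze recurrence, and no planned efficacy analysis relates baseline haze to the endpoint, although BCVA is treated differently. The primary test remains valid and its stated power stands.

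The size is modest and partly unknown. The share of eyes at 2+ is not in the documents. Under assumed shares of 20% to 40% and the recurrence gaps used above, chance imbalance contributes about 2.8 to 5.0 points within a 16.8-point half-width, and adjustment gains about 0 to 2 points of power. The main value of a change is to show whether recurrence-free means quiet. The conclusion assumes that the grade 2 entry limit means 2+ on the printed scale.

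**What to change.** Label all of the following supportive, and leave the primary chi-square test unchanged:
1. In SAP 8.1.3, add baseline study-eye haze beside the stratification factor in the logistic regression. Code it as 2+ versus below 2+, or as a linear ordinal score, so that it costs one parameter. Specify Firth or exact estimation if a cell has no events.
2. Add the same variable to the multiple imputation model (SAP 8.1.3 and the code in 13.2) and to the descriptive subgroups in 8.1.4.
3. Report, by arm, the number of eyes scored recurrence-free at Month 6 whose haze at that visit is 2+ or worse.

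The grade is already collected on Day 1 and at every visit, so no new data are needed. The cost is SAP wording, a few table rows, and one more parameter against about 26 expected events. SAP 11.2 already records edits made after unmasking, so any addition to the Month 6 analysis should carry its date and be described as supportive.

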8.2. Subject Exclusion Criteria

- Allergy to fluocinolone acetonide or any component of the FAI insert
- History of posterior uveitis only that is not accompanied by vitritis or macular edema
- History of iritis only and no vitreous cells, anterior chamber cells or vitreous haze
- Uveitis with infectious etiology
- Vitreous hemorrhage
- Intraocular inflammation associated with a condition other than noninfectious uveitis (e.g. intraocular lymphoma)
- Ocular malignancy in either eye, including choroidal melanoma
- Toxoplasmosis scar in study eye; or scar related to previous viral retinitis
- Previous viral retinitis

- Current viral diseases of the cornea and conjunctiva including epithelial herpes simplex keratitis (dendritic keratitis), vaccinia, and varicella, mycobacterial infections of the eye or fungal diseases of ocular structure
- Media opacity precluding evaluation of retina and vitreous
- Peripheral retinal detachment in area of insertion
- Diagnosis of any form of glaucoma or ocular hypertension in study eye at Screening, unless study eye has been previously treated with an incisional surgery procedure that has resulted in stable IOP in the normal range (10-21 mmHg)
- Intraocular pressure (IOP) > 21 mmHg or concurrent therapy at screening with any IOP-lowering pharmacologic agent in the study eye
- Chronic hypotony (< 6 mmHg)
- Ocular surgery on the study eye within 3 months prior to study Day 1
- Capsulotomy in study eye within 30 days prior to study Day 1
- Prior intravitreal treatment of study eye with Retisert within 36 months prior to study Day 1
- Prior intravitreal treatment of study eye with Ozurdex within 6 months prior to study Day 1
- Prior intravitreal treatment of study eye with Triesence or Trivaris within 3 months prior to study Day 1
- Prior peri-ocular or subtenon steroid treatment of study eye within 3 months prior to study Day 1
- Subjects requiring chronic systemic or inhaled corticosteroid therapy (>15mg prednisone daily) or chronic systemic immunosuppressive therapy
- Excluding certain skin cancers (specifically, basal cell carcinoma and squamous cell carcinoma), any malignancy receiving treatment, or in remission less than 5 years prior to study Day 1
- Subjects who test positive for human immune deficiency virus (HIV) or syphilis during screening
- Mycobacterial uveitis or chorio-retinal changes of either eye which, in the opinion of the Investigator, result from infectious mycobacterial uveitis
- Systemic infection within 30 days prior to study Day 1
- Any severe acute or chronic medical or psychiatric condition that could increase the risk associated with study participation or could interfere with the interpretation of study results and, in the judgment of the investigator, could make the subject inappropriate for entry into this study
- Any other systemic or ocular condition which, in the judgment of the investigator, could make the subject inappropriate for entry into this study

- Treatment with an investigational drug or device within 30 days prior to study Day 1
- Pregnant or nursing females; females of childbearing potential who are unwilling or unable to use an acceptable method of contraception as outlined in this protocol from at least 14 days prior to study Day 1 until the Month 12 Visit
- Subjects unlikely to comply with the study protocol or who are likely to be lost to follow-up within three years

